#### 8.3 Treatment of overdose

All doses upper than the planned dose will be considered as an overdose. If needed, the participant should be observed for clinical signs of dehydration and blood glucose should be monitored.

In the event of an overdose, the Investigator/treating physician should:

• Contact the Monitor (CRA) immediately.

- Closely monitor the participant for any AE/SAE and laboratory abnormalities at least for 7 days. Special attention should be paid to glycemia levels in the 24 hours,
- Document appropriately in the eCRF.

#### **8.4 Pharmacokinetics**

#### 8.4.1 Pharmacokinetic sample collection

Blood samples (one 3 mL sample per scheduled time) will be collected for the determination of concentrations of 4P-004 as planned in the study flowcharts (section 1.2). The actual time of sample collection will be recorded on the source document and eCRF.

Instructions for collecting, processing, and shipping of samples are provided in the laboratory manual.

#### 8.4.2 Bioanalytical methods

The analyses will be performed by high performance liquid chromatography (HPLC) coupled with mass spectrometry (MS) and ultraviolet-visible spectroscopy (UV).

The development and validation of the analytical method as well as the dosing of PK samples will be performed by Nuvisan GmbH ([name]) in accordance with the company's standard operating procedures and following international guidelines.

#### 8.4.3 Pharmacokinetic parameters

The following PK parameters will be calculated from measured plasma concentrations for each participant:

Maximum observed concentration (Cmax)

Time of maximum observed concentration (Tmax)

Area under the curve  $(AUC_{0-t})$ 

Half-life  $(T_{1/2})$ 

## 8.5 Visits requirements

#### 8.5.1 Screening visit, D-7 (D-14 to D-4)

The screening visit can be performed 4 to 14 days before the IMP administration.

During this visit the Investigator will:

- explain and answer all questions the participant has,
- if the participant agrees, obtain the written informed consent,
- review all inclusion / exclusion criteria, demographics, medical history and medication history,
- notify all pain killer medication taken in the past month,
- do a physical examination, including vital signs, weight and height,
- do an ECG,
- ask the participant to rate his/her pain of the target knee pain (as a mean of the previous 2 days) with the NRS
- take blood samples for clinical safety lab,

- give the participant diary to collect medical events and treatments taken up to next visit,
- give the appointment for the inclusion visit (day of IMP administration) with 24-hour hospitalization and other follow-up visits.

#### 8.5.2 Inclusion visit, D1, full day hospitalization

During this visit (24 hours hospitalization), the Investigator will:

- review inclusion / exclusion criteria, concomitant medication (from screening),
- do physical exams, ECGs, measure vital signs as per D1-D2 Study Flowchart (section 1.2.2),
- record any AE since screening,
- put a veinous line,
- remind the participant to fill in the NRS (before any study intervention on D1) for assessing target knee pain in the previous 2 days and during the hospitalization as outlined in section 1.2.2.
- randomize the participant (performed by the pharmacist)
- take blood / urine samples for glycemia, PK and OA-related biomarkers samples as per D1-D2 Study Flowchart (section 1.2.2),
- do the IA injection (modalities given in section 6.2.2 and in the Investigator manual) of the IMP extemporaneously prepared in a vial by the pharmacist (procedure for preparation is detailed in the Pharmacy manual).
- record AEs as per D1-D2 Study Flowchart (section 1.2.2),
- monitor the participant during the coming 24 hours:
  - o on local reaction as per D1-D2 Study Flowchart (section 1.2.2)
  - o on blood sugar level (veinous / capillary measures):
    - after IMP injection, glycemia will be systematically monitored (capillary measures via glucose meter and/or veinous measures) as per D1-D2 Study Flowchart (section 1.2.2),
    - when planned measurement indicates glycemia is ≤ 70 mg/dL without clinical symptom repeat the test each 30 min up to obtaining threshold value >70 mg/dL,
    - at any time if occurrence of one or more symptoms of hypoglycemia (common presenting symptoms include nausea, confusion, tremor, sweating, palpitations, or hunger), sugar will be given to the participant and a blood glycemia test should be immediately performed and closely monitored.

#### 8.5.3 Hospital discharge, D2

Before participant discharge from the hospital, the investigator or delegate will

- perform a physical exam and record vital signs,
- remind the participant
  - o to assess target knee pain [NRS] (based on the previous 24 hours) on a daily basis from D3 to the next visit date (D8),

- o to fill in the diary from D2 (after hospital discharge) up to the next visit (D8) to self-report adverse events and pain killer medication,
- give appointment for a virtual visit (phone call) at D4 ± 1d and for a face-to-face visit on D8 ± 2 days.

No specific physical limitation is recommended from the day after the injection.

In case of safety concerns after hospital discharge, the participant will be asked to call the investigator / to return to the hospital for an unscheduled safety control visit according to the investigator judgement.

## 8.5.4 Phone call (Virtual visit), D4 $\pm$ 1d

At D4 ( $\pm 1$  day), follow-up -unless abnormal, clinically significant findings are observed upon discharge or at the investigator's discretion (participants should then be brought back to the clinic for re-evaluation) will be a virtual visit by phone.

During this phone call, the Investigator or delegate will:

- review the diary with the participant,
- record adverse events if any,
- remind the participant
  - o to assess target knee pain (NRS) on a daily basis up to the next visit
  - o to self-report adverse events and pain killer medication up to the next visit,
- confirm the appointment for D8 visit.

In case of safety concerns, the participant will be asked to return to the hospital for a safety control visit.

#### 8.5.5 Follow-up visit, D8 ± 2d

During this visit, the Investigator or delegate will:

- review the diary with the participant,
- record adverse events if any,
- take a blood sample for routine tests and OA exploratory biomarkers,
- take a urine sample for exploratory biomarkers,
- remind the participant
  - o to assess target knee pain [NRS] (based on the previous 48 hours) at D15, D22 and D29,
  - o to fill in the diary for the 3 coming weeks (up to D29) to self-report adverse events and pain killer medication
- give the participant a pre-paid and pre-printed envelope for mailing back the diaries and the NRS questionnaire to the Investigator after the D29 phone call (end of study visit/virtual visit).

#### 8.5.6 EoS visit: Phone call (Virtual visit), D29 ± 2d

The Investigator or delegate call the participant by phone and will ensure that the participant completed the diary (AE, target knee pain, pain killer intake, concomitant medications) and will remind the participant to send the diary and the NRS questionnaire as planned.

The investigator will also inquire for any ongoing AEs or SAEs, worsening of AEs or SAEs, or development of new AEs or SAEs.

In case of safety concerns, the participant will be asked to return to the hospital for a safety control visit.

## 8.6 Participant compensation

For the purpose of the study, the participant will have to go 3 times to the investigational site including a day of hospitalization (day of study drug administration) for around 24 hours, during which several blood samples for PK study will be drawn. Details of compensation given to the participant are provided in the ICF.

#### 9 DATA MANAGEMENT

The sponsor or designated representative (e.g., contract research organization) will perform the data management activities in accordance with the data management plan (DMP). The DMP will outline the systems and procedures to be used in the study.

## 9.1 Data Capture

Data will be entered from the source document in an electronic CRF (eCRF, web database) by the Investigator or his/her designee. At the end of the study, each eCRF must be signed electronically by the Investigator.

#### 9.2 Access Rights

Designated personnel (Sponsor, Investigator or designee) will be provided with a personal username and password to access the eCRF database. This username/password pair may be used by a single individual only; passwords must not be shared with any other person.

#### 9.3 Audit Trail

The EDC systems developed for this study comply with the Good Clinical Practices (GCP) predicate rule requirements, laws and regulations (General Data Protection Regulation - GDPR) and allows an audit of actions performed by users. Thus, all data modifications will be documented in an audit trail file. After the last verification, the relevant data will be locked into the database. The system is also compliant with the e-signature laws (particularly the Title 21 CFR Part 11 of the Code of Federal Regulations); in that saving the data is equivalent to a handwritten signature.

#### 9.4 Data Sources

For this study, the following data sources are identified:

#### 9.4.1 Investigator's site data

These data will be directly entered into eCRF by the Investigator or his/her designee. The exhaustive list of clinical data collected at each visit will be described in the Source Data Verification List. This form will be completed and approved by the Investigator or his/her designee during Initiation visit.

#### 9.4.2 Participant reported outcome

These data are reported by the participant himself and will be entered in the eCRF. This section describes the questionnaires, note book that will be used in this study and how data will be managed (entered in eCRF or filled as paper source document).

Data to be entered in eCRF:

- NRS Questionnaire,
- Diary, including AEs/SAEs and concomitant treatments reported by the participant.

#### 9.5 Data Validation

All data entered into the eCRF will be validated by the DM. All computerized edit checks programmed to validate the data, at least on primary outcome data are described in the Data Validation Plan document, written by the DM.

Data discrepancies will trigger automatic queries, directly displayed on the screen when data entered are saved. If necessary, manual queries will be sent to the Investigator for clarification. All these discrepancies/queries have to be answered or confirmed by the site.

## 9.6 Coding

TYPE OF DATA	DATASET	DICTIONARY
Adverse Events	AE	MedDRA, most up-to-date version
Serious Adverse Events	SAE	MedDRA, most up-to-date version
Medical History	MH	MedDRA, most up-to-date version
Concomitant Medications	CM	ATC/DDD Index, most up-to-date
		version

#### 9.7 Data Lock

Clinical database will be locked after review, query resolution, signatures of the eCRF and determination that clinical database is ready for analysis.

Once the Trial is finished and database is locked, the DM should follow the database unlock/relock process to document any further change.

#### 10 STATISTICAL METHODS

#### 10.1 Statistical and analytical plans

A statistical analysis plan (SAP) will be prepared and finalized prior to database lock. This document will provide further details regarding the definition of analysis variables and analysis methodology to address all study objectives.

#### 10.1.1 Analysis sets

#### Safety set

The safety analysis set will consist of all participants who are enrolled and received 1 dose of study drug. Participants in this analysis set will be used for demographic, baseline characteristics, and safety summaries.

#### PK Set

The PK set will consist of all participants who receive study drug and have at least 1 measurable plasma concentration.

Blood samples for placebo will not be analyzed by the bioanalytical laboratory except for 2 samples per participant receiving placebo, 1 predose and the other around the expected time at which Cmax occurred (as emerging from the actual measurement of the samples of the first dose group) to ensure from a safety perspective that no additional participants could have been on active treatment.

### 10.1.2 Analysis of demographics and other baseline characteristics

Descriptive statistics (N, mean, SD, median, minimum, and maximum) will be generated for continuous demographic variables and baseline characteristics variables (age, height, weight, and BMI) for pooled placebo, each 4P-004 dose level, 4P-004 overall and overall total. The number and percentage of participants in each class of the categorical demographic variables and baseline characteristics variables (sex, ethnicity, and race) will be tabulated for pooled placebo group, each 4P-004 dose level, 4P-004 overall and overall total. Pooled placebo corresponds to participants receiving placebo in the 4 pooled cohorts.

Demographic variables will be summarized overall for participants who are screened, but not enrolled in the study. Individual demographic characteristics, date of informed consent, and reason for screen failure will be listed.

#### 10.1.3 Pharmacokinetic analysis

## Concentrations in plasma

The plasma concentration of 4P-004 will be summarized by dose level over each scheduled sampling time using descriptive statistics. Individual plasma concentration data vs time will be presented in a data listing.

## PK parameters

Descriptive statistics (N, arithmetic mean, SD, median, minimum, maximum and percent coefficient of variation [%CV]) will be used to summarize the plasma PK parameters for 4P-004 by, dose level.

### 10.1.4 Safety analysis

The safety evaluation will be based upon the review of the individual values (clinically significant abnormalities), descriptive statistics (summary tables, figures) and, if needed, on statistical analysis (appropriate estimations, confidence intervals). No statistical significance tests will be performed on safety data.

Potentially clinically significant abnormality (PCSA) values are defined as abnormal values considered medically important by the Sponsor, according to predefined criteria/thresholds based on literature reviews and defined by the Sponsor for clinical laboratory tests, vital signs, and ECG parameters.

All safety data will be presented in listings and will be summarized by placebo, each 4P-004 dose level, 4P-004 overall, and overall total.

## AEs

All AEs will be coded by system organ class (SOC) and preferred term (PT) using the Medical Dictionary for Regulatory Activities (MedDRA). Clinical judgment should be used to determine the severity of AEs as described in Section 11.3.4.

TEAEs with onset occurring within 7 days (onset date – date of dose +  $1 \le 7$ ) after study drug administration will be listed and included in the summary tables. TEAEs will be summarized by SOC and PT. The following summary tables will be included in the report: summary of TEAEs and drug-related AEs, relationship of AEs to study drug (related vs not-related), severity of AEs and related AEs. AEs leading to study drug discontinuation and SAEs will be listed. Data listings will be provided for all AEs including PTE, TEAEs, AEs leading to study drug discontinuation, and SAEs.

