## 3.2 Endpoints

#### 3.2.1 Primary endpoints

- Number of Adverse events (AEs), serious AEs (SAEs) (Common Terminology Criteria Adverse Events [CTC-AE]) from ICF signature to D29, including target knee pain and tenderness, erythema, swelling, local pain at injection site.
- Vital signs from D-7 to D8, ECG from D-7 to D1: Mean change, number of Potentially Clinically Significant Abnormality (PCSA), Percentage of participants with PCSA
- Laboratory changes (Red Blood Cells (RBC), White Blood Cells (WBC), Hemoglobin (Hb), platelets, alanine transaminase (ALT), aspartate transaminase (AST), glycemia, amylasemia, creatinin clearance) from D-7 to D8: Mean changes number of PCSA, Percentage of participants with PCSA.

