### 9.4 Derived and Computed Variables

For any variable, the baseline value is defined as the last observation before IMP injection.

The time will be split into 3 periods (epochs):

- before treatment (screening)
- during treatment (from IMP injection to 7 days after IMP injection date)

after treatment

The following PK parameters will be calculated from measured plasma concentrations for each participant:

- Maximum observed concentration (Cmax)
- Time of maximum observed concentration (Tmax)
- Area under the curve (AUC0-t)
- Terminal Half-life (T1/2)

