#### 12.2.1 Definitions

Adverse events will be classified in one of three categories:

- pre-treament: events that certainly started during screening
- post-treatment: events that certainly started after the treatment period
- treatment-emergent (TEAE): all other events

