#### Table TTT. Treatment-Emergent AESIs by SOC and PT

### Table TTT. Treatment-Emergent AESIs by SOC, PT and Toxicity Grade

A listing of all treatment-emergent AESI will also be provided.

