#### 12.2.6 Serious adverse events

A listing of all SAEs will be provided.

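### No planned table gives the adverse-event primary endpoint (consent to D29) by dose, and the TEAE window ends on D7 in the protocol but on D8 in the SAP

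*Protocol*

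**What the plan says.** **Endpoint.** Protocol 3.2.1 counts AEs and SAEs "from ICF signature to D29, including target knee pain and tenderness, erythema, swelling, local pain at injection site". Protocol 8.2.1 collects them from consent to the end of the study.

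**Protocol analysis.** Section 10.1.4 opens with a general promise: "All safety data will be presented in listings and will be summarized by placebo, each 4P-004 dose level", and then for active treatment overall and for the total. Its AEs paragraph says that "TEAEs with onset occurring within 7 days" (defined there as onset date minus dose date plus 1, at most 7) "after study drug administration will be listed and included in the summary tables". It goes on to name tables of drug relationship and severity, partly for AEs without the treatment-emergent qualifier. It sends all AEs, including pre-treatment events, to listings. It names no AESI tables. The Local tolerability paragraph promises that local-tolerability AEs will be summarised over time.

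**SAP.** Section 9.4 splits time into three periods, the middle one being "during treatment (from IMP injection to 7 days after IMP injection date". Section 12.2.1 sets aside events that certainly began during screening and "post-treatment: events that certainly started after the treatment period"; everything else is a TEAE. For AESIs (12.2.4), "A listing of all treatment-emergent AESI will also be provided". For SAEs (12.2.6), "A listing of all SAEs will be provided". Section 17 gives the tables, and Section 18 adds Listing 16.2.9 for AEs in the Safety population.

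**The concern.** Safety and tolerability at escalating doses is the first primary objective. A study report built from SAP Section 17 would hold no by-dose table of the AE endpoint as Protocol 3.2.1 defines it. To see AEs or SAEs outside the window by dose, a reader would have to count them from listings.

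The second matter is consistency. An AE with onset on D8 is treatment-emergent under one document and not under the other. D8 is the nominal day of Visit 3, when haematology and the main chemistry panel are repeated, so it is a natural onset date for a laboratory AE.

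The third is a summary that the protocol promises and the SAP does not plan.

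**Working it through.** **1. Tables in SAP Section 17 that report AEs**

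| Table | Content | All AEs, consent to D29? |
|---|---|---|
| 3.1 | Overview of TEAEs, with an SAE row | No |
| 3.1.1, 3.1.2, 3.1.3 | TEAEs by SOC and PT; by grade; by relationship | No |
| 3.2, 3.2.1 | Treatment-emergent AESIs | No |
| 3.3 | Injection site reactions, by maximum grade | No (one type of event) |

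Six of the seven are treatment-emergent by title. Table 3.3 is not so labelled, but it is not a count of all AEs. Result: 0 of 7 give the endpoint.

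**2. Where an event that certainly starts after the window appears**

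- SAE: Listings 3.4 and 16.2.9 (deaths also in Listing 3.5). The only by-dose SAE count is the SAE row of the TEAE overview.
- Non-serious AESI: Listing 16.2.9, because the AESI listing is itself treatment-emergent. An injection site reaction may also enter Table 3.3.
- Any other AE: Listing 16.2.9.

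Pre-treatment AEs are likewise outside the six tables.

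**3. Last day of the TEAE window** (dose on D1, onset on study day d)

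- Protocol 10.1.4: d − 1 + 1 ≤ 7, so d ≤ 7. The window is D1 to D7, which reproduces the stated 7 days.
- SAP 9.4: d − 1 ≤ 7, so d ≤ 8. The window is D1 to D8, or 8 days.

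The difference is one day, D8.

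**4. Calendar coverage of D1 to D29**

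- After the protocol window: 29 − 7 = 22 days; 22/29 = 76%.
- After the SAP window: 29 − 8 = 21 days; 21/29 = 72%.
- Whole endpoint period with consent 4 to 14 days before dosing: 4 + 29 = 33 to 14 + 29 = 43 days. The protocol window covers 7/43 to 7/33 (16% to 21%) and the SAP window 8/43 to 8/33 (19% to 24%).

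**5. Visit 3.** At D8 ± 2 it may fall on D6, D7, D8, D9 or D10. Three of these five days lie after the protocol window and two after the SAP window. A visit held exactly on D8 is where the documents disagree.

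**6. Local tolerability.** Protocol 10.1.4 promises a summary over time. SAP 12.2.5 and Table 3.3 give maximum grade, and Section 17 lists no over-time table for these events.

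**The case against.** The strongest reply is that consent to D29 is a collection period. The vital-sign and ECG endpoints in Protocol 3.2.1 carry similar spans that include pre-dose visits, and TEAE tables backed by listings of all AEs are an ordinary reporting choice. A focus on 7 or 8 days after a single dose is also defensible: at the 13-hour subcutaneous half-life in Protocol 2.1, 7 days is 168/13, or about 13 half-lives. Pre-treatment AEs by dose say little about tolerability. The trial is small, and SAP 9 relies on review of individual values as well as summaries.

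Much of this stands as a case for keeping the TEAE tables. It does not supply a by-dose count of what the protocol calls primary. Protocol 2.3 also says that no human safety data exist for the intra-articular route, so the systemic half-life does not settle the matter for local or delayed effects.

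On the window, the protocol's prose alone could be read as reaching D8; its formula gives D7. Protocol 10.1 leaves variable definitions to the SAP, so programming would probably use D8. That limits the consequence but leaves the documents in disagreement. Any fixed window has an edge. SAP 12.2.1 keeps uncertain onsets as TEAEs, and Visit 3 laboratory values and PCSAs are tabulated by dose regardless.

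Stronger readings that a reader might infer, and that the documents do not support:

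- *The protocol confines AE tables to TEAEs.* It says that they are included and never says that other events are excluded. The six tables are the SAP's.
- *Every late AESI is confined to one general listing.* A serious one is also in Listing 3.4, and an injection site reaction may be in Table 3.3.
- *Visit 3 is the only post-dose chemistry.* Glycaemia is measured repeatedly on D1 and D2.

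**Conclusion.** The point holds. As written, the plan yields no by-dose table of AEs and SAEs from consent to D29, although Protocol 3.2.1 makes that count a primary endpoint and Protocol 10.1.4 promises by-dose safety summaries. The firm conflict is between those two protocol statements and the SAP's table list; the protocol's AEs paragraph is compatible with the SAP but does not itself impose the restriction. The D7/D8 mismatch and the missing local-tolerability summary are also real.

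The size is modest. It would be wrong to infer that about three quarters of the events go untabulated: 72% and 76% are shares of calendar days. The documents give no AE rates, so the number of events affected cannot be computed and may be small. It would be equally wrong to infer that late events are lost. AEs in dosed participants are listed, and knee pain scores are tabulated to D29 in Table 4.2. The day counts assume dosing on D1 and the final contact on D29; with that contact on D27 to D31, the share after the window is 74% to 77% (protocol) or 70% to 74% (SAP).

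This should be fixed, but it is a reporting gap and not a flaw in safety monitoring.

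**What to change.** 1. Add one by-dose table giving the number of participants with AEs and SAEs, and the number of such events, from consent to D29. Split it into pre-treatment, treatment-emergent and post-treatment, and label it as the primary-endpoint table. Keep the TEAE tables as a subset.
2. Reconcile Protocol 10.1.4 and SAP 9.4 to one TEAE window, with its last day stated as a study-day number.
3. Add the over-time summary of local-tolerability AEs that Protocol 10.1.4 promises.

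The cost is a wording change in SAP 9.4 and 12.2, a recorded clarification of Protocol 10.1.4, and a few descriptive tables from data already collected. Reported AE counts may be somewhat higher. SAP 6.2 bars database lock before the SAP is approved, so the change can be prespecified if lock has not occurred.
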